### 6.1.2 DOSING AND ADMINISTRATION

Iron dextran shall be administered intravenously as a single dose of 1000 mg (25 mg test dose followed by 975 mg completion dose). EPO shall be administered as a single dose of 40,000 units subcutaneously. There is no patient-specific dose selection. Doses do not need to be modified in relation to meals.

## 6.2 PREPARATION/HANDLING/STORAGE/ACCOUNTABILITY

### 6.2.1 ACQUISITION AND ACCOUNTABILITY

This is a multifaceted intervention. Optimized phlebotomy will be coordinated by direct communication to the phlebotomy team by trained study personnel. Clinical decision support will be similarly coordinated by study coordinators. If a patient is randomized to the intervention arm, study coordinators will contact the research pharmacy regarding the need for IV iron +/- EPO. This will be distributed from the research pharmacy to the patient's bedside followed by administration by the bedside critical care nurse. Study coordinators will be available to ensure appropriate administration. Any unused and untampered agents will be immediately returned to the pharmacy.

### 6.2.2 FORMULATION, APPEARANCE, PACKAGING, AND LABELING

Low molecular weight iron dextran (INFeD®, AbbVie, Inc.), details from package insert: INFeD (iron dextran injection USP) is a dark brown, slightly viscous sterile liquid complex of ferric hydroxide and dextran for intravenous or intramuscular use. Each mL contains the equivalent of 50 mg of elemental iron (as an iron dextran complex), approximately 0.9% sodium chloride, in water for injection. Sodium hydroxide and/or hydrochloric acid may have been used to adjust pH. The pH of the solution is between 5.2 and 6.5.

EPO (Retacrit®, Hospira, Inc), details from package insert: Epoetin alfa-epbx is a 165-amino acid erythropoiesis-stimulating glycoprotein manufactured by recombinant DNA technology. It has a molecular weight of approximately 30,400 daltons and is produced in Chinese Hamster Ovary (CHO) cell line. The product contains the identical amino acid sequence of isolated natural erythropoietin. RETACRIT (epoetin alfa-epbx) injection for intravenous or subcutaneous administration is a sterile, clear, colorless solution in single-dose vials, formulated with an isotonic sodium chloride/sodium phosphate buffered solution. Each 1 mL single-dose vial of 2,000, 3,000, 4,000, and 10,000 Units of epoetin alfa-epbx contains calcium chloride dihydrate (0.01 mg), glycine (7.5 mg), isoleucine (1 mg), leucine (1 mg), L-glutamic acid (0.25 mg), phenylalanine (0.5 mg), polysorbate 20 (0.1 mg), sodium chloride (2.4 mg), sodium phosphate dibasic anhydrous (4.9 mg), sodium phosphate monobasic monohydrate (1.3 mg), and threonine (0.25 mg), in Water for Injection, USP. Each 1 mL vial of 40,000 Units of epoetin alfa-epbx contains calcium chloride dihydrate (0.01 mg), glycine (7.5 mg), isoleucine (1 mg), leucine (1 mg), L-glutamic acid (0.25 mg), phenylalanine (0.5 mg), polysorbate 20 (0.1 mg), sodium chloride (2.2 mg), sodium phosphate dibasic anhydrous (5.7 mg), Reference ID: 4263015 sodium phosphate monobasic monohydrate (1.5 mg), and threonine (0.25 mg), in Water

### 6.2.3 PRODUCT STORAGE AND STABILITY

Iron (INFeD®): Store at 20°C to 25°C (68°F to 77°F); excursions permitted to 15°C to 30°C (59°F to 86°F).

EPO (Retacrit®): Store at 36°F to 46°F (2°C to 8°C). Do not freeze. Do not shake. Do not use RETACRIT that has been shaken or frozen. Store RETACRIT vials in the original carton until use to protect from light.

#### 6.2.4 PREPARATION

No preparation (thawing, diluting, mixing, reconstitution) is required.

### 6.3 MEASURES TO MINIMIZE BIAS: RANDOMIZATION AND BLINDING

Participants will be randomized 1:1 to active intervention vs. standard of care using a stratified permuted block design by anemia etiology (iron responsive vs. not) and ICU admission indication (surgical vs. non-surgical). Randomization will occur electronically using the REDCap randomization module. Randomization lists will be developed by the study statisticians and uploaded directly to REDCap. Study staff involved in patient care are unable to access randomization lists in advance and therefore are unlikely to predict future randomization/assignment. Clinicians and subjects will not be blinded to study interventions. However, all data analysts will be blinded to treatment allocation while the study is ongoing.

### 6.4 STUDY INTERVENTION COMPLIANCE

Compliance will be assessed by the subject's receipt of pharmacologic therapy (iron +/- EPO). This will be assessed on study day 1 by research personnel. The proportion of subjects successfully receiving the intervention will be reported (number, %). Similarly, the proportion of subjects seen for 1-month and 3-month follow-up assessments will be reported.

### 6.5 CONCOMITANT THERAPY

For this protocol, a prescription medication is defined as a medication that can be prescribed only by a properly authorized/licensed clinician. Medications to be reported at baseline are all concomitant prescription medications, over-the-counter medications and supplements. Medications to be reported at daily visits are only to include if the subject has received iron or EPO/darbepoetin on these days.

Subjects who received iron therapies (exclusive or multivitamins with iron) or erythropoiesis stimulating agents (i.e. darbepoetin, erythropoietin) within 30 days will be excluded, as these subjects have already been receiving anemia treatment prior to enrollment.

#### 6.5.1 RESCUE MEDICINE

Not applicable

## 7 STUDY INTERVENTION DISCONTINUATION AND PARTICIPANT DISCONTINUATION/WITHDRAWAL.

### 7.1 DISCONTINUATION OF STUDY INTERVENTION

Discontinuation from the pharmacologic therapies (i.e. iron, EPO) does not mean discontinuation from the study, and remaining study procedures should be completed as indicated by the study protocol. If a clinically significant finding is identified (including, but not limited to severe allergic reactions during medication administration) after enrollment, the investigator or qualified designee will determine if any change in participant management is needed. Any new clinically relevant finding will be reported as an adverse event (AE).

The data to be collected at the time of study intervention discontinuation will include the following:

- Reason for discontinuation
- Date and time of discontinuation
- Subject-initiated or investigator-initiated discontinuation
- Changes in vital signs or clinical status that prompted discontinuation
- Adverse events

## 7.2 PARTICIPANT DISCONTINUATION/WITHDRAWAL FROM THE STUDY

Participants are free to withdraw from participation in the study at any time upon request.

An investigator may discontinue or withdraw a participant from the study for the following reasons:

- Significant study intervention non-compliance
- If any clinical adverse event (AE), laboratory abnormality, or other medical condition or situation occurs such that continued participation in the study would not be in the best interest of the participant
- If the participant meets an exclusion criterion (either newly developed or not previously recognized) that precludes further study participation

The reason for participant discontinuation or withdrawal from the study will be recorded on the appropriate Case Report Form (CRF). Subjects who sign the informed consent form and are randomized but do not receive the study intervention may be replaced. Subjects who sign the informed consent form, and are randomized and receive the study intervention, and subsequently withdraw, or are withdrawn or discontinued from the study, will not be replaced.

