## 9.4 STATISTICAL ANALYSES

### 9.4.1 GENERAL APPROACH

Baseline demographic and clinical characteristics will be presented using descriptive statistics, as applicable. Unadjusted outcome summary statistics will be described for each randomized group. Continuous variables will be summarized by mean (standard deviation), median (25th, 75th) percentiles, and range. Categorical variables will be summarized by percentage.

The primary analysis dataset consists of all randomized participants and will be analyzed using intention-to-treat (ITT) principles such that each subject is analyzed based on their allocated arm. Mortality and dropout may occur, and subjects will be analyzed as described in 9.4.2 and 9.4.3.

A secondary analysis approach may consider a per-protocol analysis, analyzing those participants who completed study procedures without major protocol violations. The per-protocol analysis definition will be finalized prior to database lock and data analysis. The ITT analysis will be considered primary.

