### 9.4.2 ANALYSIS OF THE PRIMARY EFFICACY ENDPOINT(S)

The primary outcome is hemoglobin measured repeatedly on subjects at ICU discharge, hospital discharge, and 1 month and 3 months. The longitudinal trajectory of hemoglobin will be analyzed with a LMM. The primary parameter of interest is a treatment group by time interaction to estimate the effect of treatment at each follow up time-point. The treatment effect on 1 month hemoglobin is the primary outcome; other time-points will reflect secondary outcomes. As the functional form of hemoglobin over time is unknown, a discrete time representation will be used. The model will adjust for pre-randomization hemoglobin, age, sex, anemia etiology, and medical vs surgical ICU setting to reduce residual variation and improve precision of the estimated treatment effect.

Dropout or non-response including skipped study visit and death represent two forms of missing data. Dropout or non-response unrelated to death at ICU discharge and hospital discharge is expected to be negligible but could occur with withdrawal of consent. We assume dropout (unrelated to death) while in the ICU is missing completely at random (MCAR); subjects withdrawing consent prior to observation of hemoglobin outcome at ICU discharge will be excluded from the analysis. Those dropping out after ICU discharge are assumed missing at random (MAR) with missingness possibly related to adjustment covariates, arm, or prior observed hemoglobin values. Analyses using LMM assume dropout, nonresponse, or skipped visits are MAR.

We anticipate up to 10% ICU mortality (despite exclusion of those not expected to survive hospitalization); such subjects will not have observed hemoglobin outcomes. We also anticipate additional post-ICU discharge mortality. In the primary analysis, we assume missing data due to death is MAR. Those with ICU mortality will have ICU discharge hemoglobin multiply imputed under the MAR assumption. Thereafter, LMMs assume additional missing data at other times are MAR. In secondary approaches to the analysis of hemoglobin, we use a worst-case imputation approach, to impute hemoglobins as the worst possible outcome following death. After imputation, if residuals are not reasonably normally distributed, a generalized linear mixed effects proportional odds model will be used or individual timepoints may be assessed by Wilcoxon rank-sum test without covariate adjustment.

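### Section 7.2 lets an investigator withdraw patients from the study for non-compliance, a ground only the intervention arm can meet in practice, without securing their 1-month hemoglobin

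*Combined protocol and SAP*

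**What the plan says.** Section 7.2 opens its list of grounds with "An investigator may discontinue or withdraw a participant from the study for the following reasons", and the first ground is "Significant study intervention non-compliance". It does not define the word significant. The same section allows a participant who was randomised but did not receive the intervention to be replaced. It requires the reason for a withdrawal to be recorded.

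Section 6.4 contains the only measure of compliance: "receipt of pharmacologic therapy (iron +/- EPO). This will be assessed on study day 1 by research personnel". Section 7.1, on stopping iron or EPO, says that this "does not mean discontinuation from the study, and remaining study procedures should be completed as indicated by the study protocol".

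Section 9.4.1 puts all randomised participants in the primary analysis, "such that each subject is analyzed based on their allocated arm". It also foresees a possible per-protocol analysis, "analyzing those participants who completed study procedures without major protocol violations", and 9.3 adds a secondary modified-ITT analysis.

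Section 9.4.2 treats dropout in the ICU for reasons other than death as missing completely at random (MCAR), and the only cause it names is withdrawal of consent. Later dropout is taken as missing at random (MAR), given the adjustment covariates, arm and earlier hemoglobin values.

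**The concern.** Control patients have no study drug to receive, so the 6.4 measure can be failed only in the intervention arm. The trial is open-label (6.3), and a judgement of non-compliance requires knowing the arm. Section 7.2 therefore permits a one-sided loss of participants after a single day-1 treatment, whereas 7.1 keeps patients in the study when drug is stopped.

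The primary outcome is hemoglobin 1 month after hospitalization. A patient withdrawn on day 1 leaves before the first scheduled outcome, at ICU discharge. If collection then stops, the mixed model has no post-baseline hemoglobin for that patient. An analysis labelled ITT would move toward the effect among patients who received drug. The plan already has secondary analyses for that question.

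**Working it through.** **The plan's own figures.** Section 9.2 uses SD 1.5 g/dL, target difference 1.0 g/dL, 37 per group and two-sided alpha 0.05. The two-sample t-test power is 80.8% (stated 80%). With R² = 0.25 the ANCOVA power is 90.4% (stated 90%). Inflation for dropout gives 74/(1 − 0.25) = 98.7, so 99 (stated 100). These figures reproduce and are not in dispute.

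**Is follow-up secured after an investigator withdrawal?**
- 7.1 covers a participant whose drug is stopped. It does not literally cover one who was never dosed or one withdrawn under 7.2.
- 8.1 says that all subjects return for follow-up and blood draws. It is general and does not mention withdrawn participants.
- 4.4 provides a 12-month record review for each patient, covering mortality and readmission but not hemoglobin.
- 8.3.4 and 8.3.6 keep adverse-event follow-up only.
- 9.4.2 multiply imputes ICU-discharge hemoglobin for ICU deaths and excludes early consent withdrawals. It does not address investigator withdrawals.

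None of these clearly keeps the 1-month hemoglobin after a 7.2 withdrawal.

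**When does this bias the estimate?** Missingness that depends only on arm is not MCAR. It is MAR once arm is in the model, and it does not by itself bias the contrast. Bias also needs the withdrawn patients to differ in outcome, beyond what covariates and earlier hemoglobin explain. Drug receipt could produce such a difference, and 9.4.2 does not condition on it.

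**Size, under assumed inputs.** Let k of the 50 intervention patients be withdrawn on day 1 with no later hemoglobin, and let each have 1-month hemoglobin lower by g than those retained. With everyone followed, the arm mean is lower by (k/50) × g. Losing the k patients therefore raises the estimate by

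shift = (k/50) × g.

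The documents give neither k nor g. I assume k = 2 to 5 and g = 0.5 to 1.0 g/dL, that is, half to all of the target effect lost.
- Low: (2/50) × 0.5 = 0.02 g/dL
- High: (5/50) × 1.0 = 0.10 g/dL

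Standard error of the 1-month contrast with 37 per group:
- Unadjusted: 1.5 × √(2/37) = 0.349
- With R² = 0.25: 0.349 × √0.75 = 0.302

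The shift runs from 0.02/0.349 = 0.06 to 0.10/0.302 = 0.33 standard errors.

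**Simulation check.** Settings: 1,500 trials per case, 50 per arm, four post-baseline times, SD 1.5, R² = 0.25, residual correlation 0.5, 20% background dropout at 1 and 3 months, and arm-by-time terms with a known exchangeable covariance.

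| Case | All followed | Withdrawn day 1 | Difference |
|---|---|---|---|
| 2 of 50, half the effect lost | 0.973 | 0.992 | 0.019 |
| 5 of 50, all the effect lost | 0.906 | 1.005 | 0.099 |

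**Wider inputs.** The shift is proportional to k and g. With 10 of 50 withdrawn and g = 1.5 it would be (10/50) × 1.5 = 0.30 g/dL. A g of 1.5 exceeds the whole target effect, so non-recipients would also have to be patients with a worse hemoglobin course for other reasons.

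**The case against.** The clause is permissive, and 7.2 does not itself say that a patient who misses drug is non-compliant; that reading comes from 6.4. The intervention has three components (6.1.1), and 7.1 and 7.2 can be read together, one governing drug and the other a discretionary power to end participation. Section 9.4.1 already keeps every randomised patient in the primary set. Section 8.1 points to follow-up of all subjects. It also notes that a CBC is often done daily in routine care, so discharge hemoglobin may be in the record. A patient without drug could still receive optimised phlebotomy and decision support, so losing the full 1.0 g/dL is an extreme case. Every magnitude is assumed.

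Most of this stands. It makes the conflict a tension between sections and keeps the likely effect small. It does not close the gap. Section 6.4 offers no other measure of compliance, an undefined discretionary ground in an open-label trial is a weak safeguard, and routine hospital blood counts do not supply the 1-month value.

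A reader might infer that 7.2 removes these patients from the ITT set, or that failure of MCAR is enough to bias the result. The documents support neither. Section 9.4.1 includes all randomised participants, and dependence on arm alone is handled by a model that contains arm.

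**Conclusion.** The concern holds as a minor point. Section 7.2 permits, but does not require, a withdrawal that can in practice arise in one arm only, and no section clearly preserves the primary outcome afterwards. The replacement sentence adds to the gap, because it does not say that a replaced patient keeps outcome visits.

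The shift favours the intervention if withdrawn patients would have had lower hemoglobin. At 0.02 to 0.10 g/dL it is small against the 1.0 g/dL target. That range assumes 2 to 5 of 50 withdrawn on day 1, no later hemoglobin for them, and half to all of the effect lost.

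A reader might extend the point to the 7.2 ground on newly met exclusion criteria, since thrombosis, for example, is both an exclusion (5.2) and a monitored event (8.3.1). The text does not carry that far. The ground applies only where the criterion precludes further participation, and nothing says that such an event precludes a blood draw.

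**What to change.** Reconcile 7.2 with 7.1 and 9.4.1:

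1. Remove intervention non-compliance as a ground for leaving the study. Keep it for reporting under 6.4 and for the secondary modified-ITT and per-protocol analyses.
2. State that participants who are withdrawn by an investigator or replaced stay in their allocated arm, and that hemoglobin and other outcome collection continues unless consent is withdrawn.
3. Report withdrawals by arm and reason.

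The best-interest ground in 7.2 keeps its present wording.

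The change is to wording only and leaves the sample size and visit schedule as they are. Its cost is some dilution of the ITT estimate by patients who did not receive drug, which is what ITT is meant to show. In the most adverse case above (5 of 50, all effect lost) the ITT effect is 1.0 − 0.10 = 0.90 g/dL. With 37.5 evaluable per arm (50 × 0.75), t-test power is then 72.7% and ANCOVA power 84.1%, against 81.3% and 90.8% for 1.0 g/dL. That is no reason to withdraw the patients, because the higher power belongs to an effect in those who received drug.

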## 5.2 EXCLUSION CRITERIA

An individual who meets any of the following criteria will be excluded from participation in this study:

1. IV iron or any ESA use (i.e. darbepoetin, Aranesp, erythropoietin, Epojen, Procrit, Retacrit) within 30 days of enrollment. Oral iron is permitted (e.g. oral iron supplements, multivitamin with iron)
2. Severe anemia prior to hospitalization (i.e. hemoglobin consistently  $< 9$  g/dL in the 90 days prior to admission). If hemoglobin is not available or if hemoglobin is  $\geq 9$  g/dL at any time within 90 days prior to enrollment, then this criterion is not met, and the patient may be enrolled
3. Known allergic reactions to IV iron or any EPO agent
4. Inability to complete outcome assessments (i.e. not expected to survive hospitalization, unable to make follow-up appointments, non-ambulatory status preceding hospitalization, dementia or other severe cognitive impairment, visual impairment i.e. blind or legally blind, non-English speaking)
5. Pregnancy or breastfeeding at time of enrollment given unclear safety of EPO
6. Inability to receive pharmacologic venous thromboembolic prophylaxis except in patients with acute blood loss anemia (i.e. recent surgery or gastrointestinal bleeding, extracranial bleeding)
7. Active or suspected thrombosis (i.e. DVT, pulmonary embolism, acute arterial thrombus) within 3 months except in patients with acute blood loss anemia (i.e. recent surgery, gastrointestinal bleeding, extracranial bleeding)
8. Uncontrolled sepsis (i.e. lack of definitive source control and/or  $< 48$  hours of appropriate antimicrobial therapy)
9. Having received  $\geq 10$  units of allogeneic RBCs in the 48 hours before enrollment
10. Acute coronary syndrome (STEMI or NSTEMI) or ischemic stroke within 3 months except in patients with acute blood loss anemia (i.e. recent surgery, gastrointestinal bleeding, extracranial bleeding)
11. Weight less than 40 kg
12. Concerns with study enrollment expressed by the clinical team

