## 8.3 ADVERSE EVENTS AND SERIOUS ADVERSE EVENTS

### 8.3.1 DEFINITION OF ADVERSE EVENTS (AE)

Adverse event means any untoward medical occurrence associated with the use of an intervention in humans, whether or not considered intervention-related (21 CFR 312.32 (a)).

As our subject population is by definition 'critically ill', it is expected that they will have many unrelated adverse health events during their hospital stay. Therefore, we will limit the scope of our adverse event monitoring and recording to focus on the following conditions:

- Study drug infusion reactions
- Venous thromboembolic disease
- Myocardial infarction
- Non-hemorrhagic stroke
- Bloodstream infections
- Hypertensive urgency or emergency in the 1 hour after study drug administration (i.e. SBP  $\geq$  200 or SBP increase by > 40 mmHg from the time of infusion start)

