#### 8.3.4 TIME PERIOD AND FREQUENCY FOR EVENT ASSESSMENT AND FOLLOW-UP

The occurrence of an adverse event (AE) or serious adverse event (SAE) may come to the attention of study personnel during study visits and interviews of a study participant presenting for medical care, or upon review by a study monitor.

As noted earlier, for this study we plan to observe for a specific set of AEs and this information will be captured on the appropriate case report form (CRF). Information to be collected includes event description, time of onset, clinician’s assessment of severity, relationship to study product (assessed only by those with the training and authority to make a diagnosis), and time of resolution/stabilization of the event. All AEs will be followed to adequate resolution.

Changes in the severity of an AE will be documented to allow an assessment of the duration of the event at each level of severity to be performed.

Study coordinators will record all listed reportable events with start dates occurring any time after informed consent is obtained through 3-months after hospitalization. At each study visit, the investigator will inquire about the occurrence of AE/SAEs since the last visit. Events will be followed for outcome information until resolution or stabilization.

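### Section 7.2 lets an investigator withdraw a randomised participant from the study for an exclusion criterion that arises or is recognised later; several criteria overlap with the trial's own outcomes, and no text keeps such participants in follow-up.

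*Combined protocol and SAP*

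**What the plan says.** The list in Section 7.2 opens with "An investigator may discontinue or withdraw a participant from the study for the following reasons". One ground is "If the participant meets an exclusion criterion (either newly developed or not previously recognized) that precludes further study participation". A neighbouring ground, "If any clinical adverse event (AE), laboratory abnormality, or other medical condition or situation occurs", applies where staying in the study is judged to be against the participant's interest. Both concern leaving the study. Stopping iron or EPO is dealt with in Section 7.1, which says the remaining study procedures should still be completed. Section 7.2 has no such sentence; it asks only that the reason be entered on the case report form.

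In Section 5.2, criterion 4 begins "Inability to complete outcome assessments (i.e. not expected to survive hospitalization, unable to make follow-up appointments" and goes on to include severe cognitive impairment. Criterion 7 is "Active or suspected thrombosis (i.e. DVT, pulmonary embolism, acute arterial thrombus) within 3 months", and criterion 10 covers acute coronary syndrome and ischemic stroke. Criteria 7 and 10 make an exception for acute blood loss anemia.

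Section 8.3.1 restricts recorded adverse events to a short list that includes "Venous thromboembolic disease", myocardial infarction and non-hemorrhagic stroke. Section 8.3.4 collects events starting "any time after informed consent is obtained through 3-months after hospitalization". Section 9.4.1 states: "The primary analysis dataset consists of all randomized participants".

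On blinding, Section 6.3 says clinicians and subjects are unblinded. Section 4.1 describes investigators and assessors as blinded at the post-hospital assessments. Neither says that an investigator deciding on withdrawal during the hospital stay is blinded.

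**The concern.** An exclusion criterion protects participants and data quality before randomisation. After randomisation the same condition can be a result of treatment or of the illness under study. A rule that ends participation when the condition appears lets the outcome decide who is followed.

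The pharmacologic component is a single administration at enrollment (Section 6.1.2), so ending follow-up after a later event does not reduce drug exposure. A participant for whom continuing would be harmful is already covered by the best-interest ground. The limiting phrase about precluding further participation is not defined.

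At stake are the 1-month hemoglobin (the primary endpoint), the 1- and 3-month functional and cognitive measures, and any adverse events between withdrawal and 3 months. The ground also works against the retention effort. Section 5.5 calls follow-up above 75% necessary, and Section 7.3 requires repeated contact after a missed visit, yet a participant who becomes unable to attend could instead be withdrawn under Section 7.2.

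**Working it through.** The plan gives no rate for withdrawals of this kind, so the check is mainly a comparison of sections.

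**Step 1. Overlap between criteria and outcomes.**

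| Section 5.2 criterion, if met after randomisation | What the trial measures |
|---|---|
| 4: expected in-hospital death | 12-month all-cause mortality (Section 3) |
| 4: severe cognitive impairment | MoCA-BLIND at 1 and 3 months (Section 3) |
| 4: inability to attend follow-up | Proportion seen at 1 and 3 months (Section 6.4), and the visits that supply the primary endpoint |
| 7: thrombosis | Venous thromboembolism as a recorded adverse event (Section 8.3.1) |
| 10: acute coronary syndrome or ischemic stroke | Myocardial infarction and non-hemorrhagic stroke as recorded adverse events (Section 8.3.1) |

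**Step 2. What continues after withdrawal.** Section 7.1 applies to stopping drug. Section 7.3 applies to missed visits. No section says that an investigator-withdrawn participant continues.

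- Exposed: hemoglobin, function and cognition at 1 and 3 months, and new adverse events up to 3 months, which Section 8.3.4 collects partly by asking at each visit.
- Less exposed: the triggering event, because the reason for withdrawal is recorded and Sections 8.3.4 and 8.3.6 follow known events to resolution or stability.
- Less exposed: 12-month mortality and readmission, because Section 4.4 takes these from the medical record for each patient.

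**Step 3. What the analysis does with the gap.** Section 9.4.2 assumes that dropout after ICU discharge is missing at random given covariates, arm and earlier hemoglobin. The covariates are pre-randomisation hemoglobin, age, sex, anemia etiology and ICU setting. Thrombosis, stroke and prognosis after randomisation are not among them. For non-death dropout in the ICU the assumption is missing completely at random; exclusion from analysis is described for consent withdrawal, with no rule for investigator withdrawal. Section 9.4.3 multiply imputes functional outcomes under missing at random. Section 4.1 mentions missing-not-at-random approaches for function, but the only one specified is worst-value imputation after death.

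**Step 4. Whether the arms could differ.** Section 2.3.1 cites a relative risk of 1.17 (0.87–1.58) for venous thromboembolism with EPO and says a clinically significant increase in adverse events is not excluded. Event frequency and readiness to withdraw could therefore differ by arm.

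**Step 5. Size.** If a fraction w of an arm is withdrawn and its unseen values fall short of the model's prediction by d, that arm's mean is overstated by w × d. The documents give neither w nor d.

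A power check can be made on the plan's own figures. With SD 1.5, difference 1.0 and 37 per group, the noncentrality is 1/(1.5 × √(2/37)) = 2.87 on 72 degrees of freedom. This gives 80.8% power, against the stated 80%. With SD 1.5 × √0.75 it is 90.4%, against 90%. Enrollment is 74/0.75 = 98.7, so 99, against 100 planned. The 25% allowance names death and loss to follow-up, not investigator withdrawal. If an assumed further 2%, 5% or 10% were lost, 36.5, 35.0 or 32.5 per arm would remain and t-test power would be 80.2%, 78.5% or 75.4%, against 81.3% at 37.5 per arm. At the low end of that range little power is lost; the main issue is who is lost.

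**The case against.** The strongest reply is that the rule is permissive and qualified. An investigator may withdraw, and only if the criterion precludes participation. A thrombosis after a single dose need not preclude a blood draw or a chart review, so sensible investigators would rarely use the ground this way. That is fair, and it limits how often harm would occur. It does not supply the missing sentence on follow-up, and the qualifier is undefined.

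Three stronger readings are tempting, and the documents do not support them.

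- *A reader might infer that a mortality excess would be hidden because withdrawn participants are censored at the event.* Section 9.4.3 censors at last contact with the health system, and only when 1-year status is unknown; Section 4.4 extracts that status from the record; inclusion criterion 6 restricts entry to patients embedded in that system. Figures for such an effect also need assumed rates. With events in 12% versus 6% and mortality of 40% after an event versus 15% otherwise, the excess is 0.06 × 0.25 = 1.5 points. That doubling of risk exceeds the upper limits in Section 2.3.1 (1.58 for venous thromboembolism, 1.31 for serious adverse events). With the same 6% and 25-point gap, relative risks of 1.17 and 1.58 give about 0.26 and 0.87 points, and losing even those would need every such participant to be withdrawn and censored.
- *A reader might infer that withdrawn participants leave the intention-to-treat set.* Section 9.4.1 keeps all randomised participants and refers dropout to the missing-data rules. What may be lost is their outcomes.
- *A reader might infer that a cognitive benefit would be erased.* A low MoCA-BLIND score is not itself a trigger. Imputation under missing at random could attenuate a benefit; nothing shows that it would remove it.

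The reply also notes, correctly, that deleting this ground alone would leave the adverse-event ground able to end follow-up for the same participant. The fix has to cover both.

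**Conclusion.** The point holds as a gap in follow-up protection. Section 7.2 permits outcome-related, and possibly arm-related, loss of the 1- and 3-month assessments and of later adverse event capture, and the planned analysis does not address that loss beyond assuming it is ignorable. If withdrawn participants do worse than the model predicts, the arm with more withdrawals looks better than it is.

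No numerical magnitude is claimed. The conclusion rests on three assumptions: that the ground is used at least occasionally, that withdrawal from the study means visits stop, and that the person deciding may know the allocation. The documents leave each of these open. The mortality and readmission comparisons are not shown to be compromised.

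**What to change.** In Section 7.2, remove the exclusion-criterion ground as a reason for withdrawal from the study. Add a statement covering every investigator-initiated discontinuation, including on the adverse-event ground:

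- the participant remains in the intention-to-treat set;
- the 1- and 3-month hemoglobin and functional assessments, adverse event capture to 3 months and the 12-month record review continue, unless the participant or proxy withdraws consent, or a specific procedure is judged not to be in the participant's interest.

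Record late-recognised ineligibility as a protocol deviation under Section 10.1.10.

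The cost is a short protocol amendment and continued follow-up of a few participants at visits already planned. Section 5.5 notes that the core functional measures other than the 6-minute walk can be done by telephone, which helps where attendance is the difficulty. The sample size does not change.
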